5. ANALYSIS SETS

5.1. Definition

5.1.1. Total vaccinated cohort (TVC)

The Total vaccinated cohort for the primary epoch will include all subjects who received at least one primary vaccine dose. Thus, the Total vaccinated cohort for analysis of safety of the primary epoch will include all subjects with at least one primary vaccine dose administration documented and the Total vaccinated cohort for analysis of immunogenicity will include vaccinated subjects for whom data concerning primary immunogenicity endpoint measures are available.

The Total vaccinated cohort for the booster epoch will include all subjects who received the booster vaccine dose. Thus, the Total vaccinated cohort for analysis of immunogenicity for the booster epoch will include vaccinated subjects for whom data concerning booster immunogenicity endpoint measures are available.

5.1.2. According-to-protocol cohort for analysis of immunogenicity of the primary epoch

The ATP cohort for analysis of immunogenicity of the primary epoch will include all evaluable subjects (i.e. those meeting all eligibility criteria, complying with the procedures and intervals relative to the primary epoch defined in the protocol, with no elimination criteria during the primary epoch of the study) for whom data concerning primary immunogenicity endpoint measures are available. This will include subjects for whom assay results are available for antibodies against at least one study vaccine antigen component one month after Dose 3. The interval between Dose 3 and blood sampling at Visit 4, considered for inclusion of a subject will be 21-48 days.

5.1.3. Total vaccinated cohort for the booster epoch

The Total vaccinated cohort for the booster epoch will include all subjects who received the booster dose of study vaccine.

- The TVC for the analysis of safety of booster epoch will include all subjects with booster vaccine dose administration documented.
- The Total vaccinated cohort for analysis of immunogenicity of the booster epoch will include vaccinated subjects for whom data concerning booster immunogenicity endpoint measures are available.

5.1.4. According-to-protocol cohort for analysis of immunogenicity of the booster epoch

- The ATP cohort for analysis of immunogenicity of the booster epoch will include all evaluable subjects (i.e. those meeting all eligibility criteria, complying with the procedures and intervals relative to the booster epoch defined in the protocol, with no elimination criteria during the primary and booster epoches of the study) for whom data concerning immunogenicity endpoint measures of booster epoch are available. This will include subjects for whom assay results are available for antibodies against at least one study vaccine antigen component one month after the booster dose of vaccination. The interval between study visits that will be considered for inclusion in the ATP cohort for immunogenicity of booster epoch will be 15–18 months from date of birth to booster vaccination visit and 21-48 days between the booster vaccination visit and the blood sampling at one month post-booster vaccination.

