3. STUDY DESIGN OVERVIEW

Study Group:	DTPa-IPV/Hib Group (N=235)					
Study Vaccine:	Infanrix-IPV/Hib					
Visit:	Visit 1	Visit 2	Visit 3	Visit 4	Visit 5	Visit 6
Time-points:	Day 0	Month 1.5	Month 3	Month 4	Month 15	Month 16
Age of subjects:	3 months	4.5 months	6 months	7 months	18 months	19 months
Vaccination and BS:	V1	V2	V3	Post-Pri BS	Booster	Post-Booster BS
Epochs:	← Primary epoch →				← Booster epoch →	

V = Primary vaccination

BS = Blood Sample

Post-Pri = One month after the third dose of primary vaccination course

Post-Booster = One month after booster vaccination

Protocol waivers or exemptions are not allowed with the exception of immediate safety concerns. Therefore, adherence to the study design requirements, including those specified in the outline of study procedures (Section 5.5), are essential and required for study conduct.

- Experimental design: Phase III, open-label, multi-centric, single-country study with a single group.
- Duration of the study: The intended duration of the study is approximately 16 months, per subject.
 - Epoch 001 (Primary epoch): Primary phase starting at Visit 1 (Day 0) and ending at Visit 4 (Month 4).
 - Epoch 002 (Booster epoch): Booster phase starting at Visit 5 (Month 15) and ending at Visit 6 (Month 16).

Study group: The study group and epochs foreseen in the study are presented in Table 1.

Table 1 Study group and epochs foreseen in the study

Study group	Number of subjects	Age (Min/Max)	Epochs	
			Epoch 001 (Primary epoch)	Epoch 002 (Booster epoch)
DTPa-IPV/Hib Group	~ 235	3 months - 4 months	x	
DTPa-IPV/Hib Group	~ 235	18 months – 19 months		x

The study group and treatment foreseen in the study are presented in Table 2.

Table 2 Study group and treatment foreseen in the study

Treatment name	Vaccine/Product name	Study Group
		DTPa-IPV/Hib Group
Infanrix-IPV/Hib	DTPa-IPV	x
	Hib	x

- Control: uncontrolled.
- Treatment group and vaccination schedule: All subjects will receive three doses of primary vaccination at 3, 4.5 and 6 months of age and a single dose of booster vaccination at 18 months of age.
 - DTPa-IPV/Hib Group: Subjects who will receive DTPa-IPV/Hib vaccine (*Infanrix-IPV/Hib*).
- Blinding: This is an open-label study (Refer Table 3).

Table 3 Blinding of study epochs

Study Epochs	Blinding
Epoch 001 (Primary epoch)	open
Epoch 002 (Booster epoch)	open

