● is used to indicate a study procedure that requires documentation in the individual eCRF.

○ is used to indicate a study procedure that does not require documentation in the individual eCRF.

Refer to Section 8.1.3.1 and 5.6.10 for detailed explanation on the reporting of large injection site reactions

The intervals between study visits are presented in Table 5. These intervals determine each subject's evaluability in the according-to-protocol analyses.

Table 5 Intervals between study visits

Interval	Optimal length of interval ¹	Allowed interval ²
Birth → Visit 1	90 days	90-120 days
Visit 1 → Visit 2	45 days	28-62 days
Visit 2 → Visit 3	45 days	28-62 days
Visit 3 → Visit 4	30 days	21-48 days
Birth → Visit 5	540 days	540-570 days
Visit 5 → Visit 6	30 days	21-48 days

¹ Whenever possible the investigator should arrange study visits within this interval.

² Subjects will not be eligible for inclusion in the analyses of the according-to-protocol (ATP) cohort of immunogenicity for the respective epochs if they make the study visit outside this interval. An interval of 21-48 days between Visit 3 and Visit 4, and between Visit 5 and Visit 6 will be considered for the ATP cohort of immunogenicity for the analysis of respective epochs. Refer Section 10.4 for the definition of the cohorts for analysis.

If a subject returns for the Visit 4 or the Visit 6 blood draw prior to completion of the 31-day safety follow-up period, the subject should continue to record this information in the diary card until 31 days post-vaccination and mail the diary card to the site. The investigator will make an attempt to obtain this information as soon as possible after the 31-day follow-up period if it is not mailed in.

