5.1.5. Adapted ATP cohort

Adapted ATP cohort for analysis of immunogenicity will be used for tables presenting immunogenicity data from both the primary and booster epoch to indicate that the ATP cohort for analysis of immunogenicity of the primary epoch is used for endpoint at visit 4 (one month post primary) and that the ATP cohort for analysis of immunogenicity of the booster epoch is used for endpoints at visit 6 (one month post booster).

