5.2. Criteria for eliminating data from Analysis Sets

Elimination codes are used to identify subjects to be eliminated from analysis. Detail is provided below for each sets.

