2070	Concomitant infection not related to the vaccine which may influence immune response => Subjects may be eliminated from the ATP cohort for immunogenicity if, during the study, they incur a condition that has the capability of altering their immune response (i.e. pertussis infection) or are confirmed to have an alteration of their initial immune status.
2080	Non-compliance with vaccination schedule =>
	Subjects who did not comply with the vaccination interval of 28-62 days between doses
	age outside of (540-570 days) at the time of the booster vaccination

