11.2.3. Demography

Age: Age at the reference activity, computed as the number of complete weeks between the date of birth and the reference activity.

Conversion of weight to kg: the following conversion rule is used:

Weight in Kilogram= weight in Pounds / 2.2 + weight in ounces / 35.2

The result is rounded to 2 decimals.

Conversion of height to cm: the following conversion rule is used:

Height in Centimetres = Height in Feet * 30.48+

Height in Inch * 2.54

The result is rounded to the unit (ie no decimal).

Conversion of temperature to °C: the following conversion rule is used:

Temperature in °Celsius = ((Temperature in °Fahrenheit -32) *5)/9

The result is rounded to 1 decimal.

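### The booster ATP cohort's 15–18-month rule overlaps the 540–570-day booster window on as few as 1 of 31 days, so read literally it could exclude many children boosted on schedule

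*SAP*

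**What the plan says.** Two rules govern age at the booster for entry to the booster ATP immunogenicity cohort.

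- **Month rule.** SAP 5.1.4 and Protocol 10.4.4, in the same words, admit subjects with "15–18 months from date of birth to booster vaccination visit".
- **Day rule.** Protocol Table 5 (Section 5.5) allows 540–570 days from birth to Visit 5, with day 540 as the optimum. Its second footnote gives this interval analytic force: "Subjects will not be eligible for inclusion in the analyses of the according-to-protocol (ATP) cohort of immunogenicity for the respective epochs" if the visit falls outside it. SAP 5.2.2.2, code 2080, eliminates subjects with "age outside of (540-570 days) at the time of the booster vaccination".

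Table 1 in both documents describes the booster epoch as 18 to 19 months of age, in line with the day rule.

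SAP 5.1.4 also requires compliance with the protocol's intervals and subjects "with no elimination criteria during the primary and booster epoches of the study". As written, a child must satisfy both rules.

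The SAP's only age derivation (11.2.3) has age "computed as the number of complete weeks between the date of birth and the reference activity". Nothing converts months to days. SAP Section 9, which lists departures from the protocol, does not mention the conflict.

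**The concern.** The month rule ends about where the day rule begins. A child boosted well inside the allowed window can be older than 18 months and so fail the cohort definition. Because Table 5's optimal day is also its first allowed day, any delay within the window moves a child towards exclusion under the month rule.

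This cohort is the main analysis set for post-booster seroprotection, seropositivity and GMC/GMT results. It also feeds the combined tables, since under SAP 5.1.5 "the ATP cohort for analysis of immunogenicity of the booster epoch is used for endpoints at visit 6". Its size, and so the precision of every main Visit 6 estimate, depends on which sentence the programmer follows and how that person reads 18 months.

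**Working it through.** **Inputs**

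- Month rule: 15–18 months (SAP 5.1.4, Protocol 10.4.4).
- Day rule: 540–570 days (Table 5, code 2080), which is 570 − 540 + 1 = 31 days.
- Protocol 4.2 equates 3 to 4 months with 90 to 120 days, implying 30-day months.
- 200 evaluable and 235 enrolled (Protocol 10.3). The 200 is the plan's general target; no separate booster figure is given.
- A complementary TVC analysis is triggered when more than 5% of enrolled subjects are excluded (Protocol 10.7, SAP 6.3.1).

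**Step 1. Reproduce the plan's figures.** With 30-day months, 18 × 30 = 540 and 19 × 30 = 570, so Table 5 matches Table 1's 18–19 months exactly. When all n subjects respond, the Clopper-Pearson lower limit is 0.025^(1/n). For n = 200 this gives 98.2%, as in Protocol Table 16.

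**Step 2. Count window days at or below 18 months.** The 15-month end never binds, because every window day lies above it.

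| Reading of 18 months | Last day admitted | Days kept of 31 |
|---|---|---|
| 30-day months | 18 × 30 = 540 | 1 (3.2%) |
| Average months | 18 × 30.4375 = 547.9, so day 547 | 8 (25.8%) |
| Calendar anniversary | day 546 to 550, by birth date | 7–11 (22.6–35.5%) |
| 18 completed calendar months | before day 577 to 581 | 31 (100%) |
| 18 completed 30-day months | before day 570 | 30 (96.8%) |

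**Step 3. Effect on the cohort.** The documents give no distribution of booster ages, so this is a range under assumptions: 200 otherwise evaluable children, all responding.

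*No loss:* completed calendar months, or every visit on day 540. n = 200, lower limit 98.2%.

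*Visits spread evenly over the window:* n = 200 × (days kept)/31.

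| Reading | Loss | n | Exact 95% lower limit |
|---|---|---|---|
| Average months | 74% | 52 | 93.2% |
| Calendar anniversary | 65–77% | 71 to 45 | 94.9% to 92.1% |
| 30-day months | 97% | 6 | 54.1% |

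*Visits clustered just after day 540:* weights exp(−d/s) for delays d = 0 to 30 days, with s from 3 to 14 (mean delay 2.5 to 9.7 days).

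| Cut-off | Loss | n | Exact 95% lower limit |
|---|---|---|---|
| Day 547 | 6.9–51.1% | 186 to 98 | 98.0% to 96.3% |
| Day 540 | 71.7–92.3% | 57 to 15 | 93.7% to 78.2% |

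**Step 4. TVC trigger.** 0.05 × 235 = 11.75, so 12 or more exclusions bring in the second analysis.

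**The case against.** The strongest reply is that the month rule will not be what is run. SAP 5.2 says "Elimination codes are used to identify subjects to be eliminated from analysis", and code 2080 is the only code with a booster-age condition; no code carries 15–18 months. On that view the cohort sentence is an inconsistent leftover and nobody is lost. This is plausible, and it means the loss is possible rather than shown. It does not remove the defect: the set analysed would then differ from its definition in both documents.

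Second, reading 18 months as completed months is ordinary usage and removes all or nearly all of the loss. That stands as a possibility, and the SAP's use of completed weeks lends it some support. But neither document adopts that reading. The 30-day month behind the 1-in-31 figure is likewise inferred from the protocol's pairings of months and days, not defined.

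Third, the consequences are bounded. The booster endpoints are secondary, everything is descriptive, there is no success criterion, and a sizeable loss would bring in the TVC analysis. All of this stands and limits the severity. The TVC analysis only complements the ATP result, which remains the main one.

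Finally, the visit-age distributions used above have no source in the documents. They illustrate a range and are not forecasts. The contradiction does not depend on them.

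**Conclusion.** The concern holds. Two written rules for the same cohort conflict, in the protocol and in the SAP, and a reader who applies both would drop children boosted within the allowed window. The overlap runs from 1 of 31 days to the full window, depending on an undefined month convention. The corresponding loss runs from none to about 97%, assuming 200 otherwise evaluable children and, at the upper end, visits spread evenly with 30-day months. The actual loss cannot be predicted from the documents and may be zero if code 2080 is what is programmed. This should be fixed, but it does not threaten the trial's primary objective.

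**What to change.** Before the booster analysis, reconcile Protocol 10.4.4, SAP 5.1.4, Protocol Table 5 and SAP code 2080 so that one booster-age interval, stated in days, appears identically in each. Which interval that should be is for the sponsor to settle. One way is for the cohort sentence to refer to the visit-interval table rather than give its own figure in months. Record the change in SAP Section 9.

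The cost is one SAP sentence and one line in Section 9, with a matching correction to Protocol 10.4.4. Section 9 already documents corrections to protocol errors, including this cohort's reference to an undefined ATP safety cohort, so the SAP entry need not wait for the protocol text. No new data are needed.

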5.1.5. Adapted ATP cohort

Adapted ATP cohort for analysis of immunogenicity will be used for tables presenting immunogenicity data from both the primary and booster epoch to indicate that the ATP cohort for analysis of immunogenicity of the primary epoch is used for endpoint at visit 4 (one month post primary) and that the ATP cohort for analysis of immunogenicity of the booster epoch is used for endpoints at visit 6 (one month post booster).

5.2. Criteria for eliminating data from Analysis Sets

Elimination codes are used to identify subjects to be eliminated from analysis. Detail is provided below for each sets.

5.2.1. Elimination from Total vaccinated cohort (TVC)

Code 1030 (Study vaccine not administered at all) and code 900 (invalid informed consent or fraud data) will be used for identifying subjects eliminated from TVC. The epoch indicator (PR for primary, BO for booster) will be used to indicate the epoch for which data was eliminated.

5.2.2. Elimination from ATP cohort for immunogenicity

5.2.2.1. Excluded subjects

A subject will be excluded from the ATP cohort for immunogenicity under the following conditions

Code	Decode => Condition under which the code is used
900	Questionable subject => Invalid informed consent or fraudulent data. In case informed consent is obtained retrospectively the subject is not eliminated.
1030	Study vaccine dose not administrated at all but subject number allocated => subjects enrolled but not vaccinated
2010	Protocol violation (inclusion/exclusion criteria) => ineligible subject: age outside of (90-120 days) at the time of the first vaccination Other considerations as stated in section 4.2 – 4.3 in the protocol
2120	Obvious incoherence or abnormality or error in data => BS result available while BS not taken Post booster results below post-primary results for all available assays tested

5.2.2.2. Right censored Data

Code	Decode => Condition under which the code is used
1040	
Administration of vaccine(s) forbidden in the protocol =>
 
Use of an investigational or non-registered product (drug or vaccine) other than the study vaccine used during the study period.
 
A vaccine not foreseen by the study protocol administered during the period starting from 30 days before each dose of vaccine and ending 30 days after*, with the exception of hepatitis B vaccine and other vaccines given as part of the national immunisation schedule, that are allowed at any time during the study period. Seasonal or pandemic influenza vaccine can be given at any time during the study, and according to the Summary of Product Characteristics and national recommendations.
 
*In case an emergency mass vaccination for an unforeseen public health threat (e.g.: a pandemic) is organised by the public health authorities, outside the routine immunisation program, the time period described above can be reduced if necessary for that vaccine provided it is licensed and used according to its SmPC or Prescribing Information and according to the local governmental recommendations and provided a written approval of the Sponsor is obtained.

1070	
Study vaccine dose not administered according to protocol =>
 
Route of vaccination is not Intramuscular for DTPa-PV/Hib
 
Incomplete vaccination course of DTPa-PV/Hib regardless of dropout.
 
Wrong reconstitution of the DTPa-PV/Hib before injection

1080	Vaccine temperature deviation => DTPa-PV/Hib vaccine administered despite a Good Manufacturing Practices (GMP) no-go temperature deviation
1090	Expired vaccine administered=> Subjects who received an expired DTPa-PV/Hib vaccine
2040	
Administration of any medication forbidden by the protocol:=>
 
Long-acting immune-modifying drugs administered at any time during the study period (e.g. infliximab).
 
Use of immunosuppressants or other immune-modifying drugs administered chronically (i.e., more than 14 days) during the study period. For corticosteroids, this will mean prednisone ≥ 0.5 mg/kg/day, or equivalent. Inhaled and topical steroids are allowed.
 
Immunoglobulins and/or any blood products administered during the study period..

2070	Concomitant infection not related to the vaccine which may influence immune response => Subjects may be eliminated from the ATP cohort for immunogenicity if, during the study, they incur a condition that has the capability of altering their immune response (i.e. pertussis infection) or are confirmed to have an alteration of their initial immune status.
2080	Non-compliance with vaccination schedule =>
	Subjects who did not comply with the vaccination interval of 28-62 days between doses
	age outside of (540-570 days) at the time of the booster vaccination

5.2.2.3. Visit-specific censored Data

Code	Decode => Condition under which the code is used
2090	Non-compliance with the blood sampling schedule (including wrong and unknown dates) => Blood sample not collected within 21 days-48 days after the booster dose of the DTPa-PV/Hib vaccine (Visit 6). Blood sample not collected within 21 days-48 days after the third dose of the DTPa-PV/Hib vaccine (Visit 4).
2100	Essential serological data missing => No serological results at all available post-primary (Visit 4) No serological results at all available post-booster (Visit 6) or at

5.3. Important protocol deviation not leading to elimination from ATP cohort for immunogenicity

Refer to the protocol deviation management plan for important protocol deviation not leading to elimination from ATP cohort for immunogenicity.

6. STATISTICAL ANALYSES

Note that standard data derivation rule and stat methods are described in Section 11 and will not be repeated below.

6.1. Demography**6.1.1. Analysis of demographics/baseline characteristics planned in the protocol**

The analysis of demographics will be performed separately for each epoch:

- The distribution of subjects enrolled among the study centers will be tabulated.
- The number of subjects who withdraw from the study will be tabulated according to the reason for drop-out.
- The deviations from specifications for age and intervals between study visits will be tabulated.

The median, mean, range and standard deviation of age (in weeks) at each vaccine dose will be computed. The median, mean and standard deviation of height in centimeter (cm) and weight in kilograms (kg) at Visit 1 will be computed. The Body Mass Index (BMI) at Visit 1 will also be computed as weight (in kg) / height² (in meters). The gender composition and geographic ancestry will be presented.

6.1.2. Additional considerations

The distribution of subjects enrolled among centers and the summary of subjects withdrawal will be generated for the full study on the total vaccinated cohort. All demography summaries will be generated for the TVC and the 2 ATP cohorts. This will include BMI, gender composition and geographic ancestry. Age at first primary vaccination and age at booster vaccination will be computed in weeks.

Number and reason for elimination from each ATP cohort will be tabulated.

6.2. Exposure

6.2.1. Analysis of exposure planned in the protocol

Not applicable

6.2.2. Additional considerations

The number of doses administered will be tabulated.

6.3. Immunogenicity

6.3.1. Analysis of immunogenicity planned in the protocol

The analysis of immunogenicity will be performed separately for each epoch.

The primary analysis will be based on the ATP cohort for analysis of immunogenicity for both primary and booster epochs. If the percentage of enrolled subjects excluded from this ATP cohort is more than 5%, a second analysis based on the Total vaccinated cohort will be performed on both primary and booster epochs to complement the ATP analysis. All analyses are descriptive.

Where appropriate, at each time-point that a blood-sample result is available:

- Seroprotection rates against diphtheria toxoid, tetanus toxoid, PRP antigen and poliovirus types 1, 2 and 3 antigens (with exact 95% CI) will be calculated.
- Seropositivity rates against PT, FHA and PRN antigens (with exact 95%) will be calculated.
- GMCs/GMTs with 95% CI will be tabulated for antibodies against each antigen.

The distribution of antibody concentrations/titres for each antigen will be displayed using reverse cumulative distribution curves (RCCs).

Handling of missing data:

- For a given subject and a given immunogenicity measurement, missing or non-evaluable measurements will not be replaced. Therefore, analyses will exclude subjects with missing or non-evaluable measurements.

